1. INTRODUCTION

1.1 Abstract

Bacterial vaginosis (BV) is the most common cause of vaginal discharge among reproductive aged women in the United States. It has an estimated prevalence of 30% or nearly 1 in 3 reproductive aged women. BV is an established risk factor for adverse outcomes in pregnancy, including preterm labor, preterm premature rupture of membranes, and chorioamnionitis, all of which increase the risk of postpartum complications including endometritis and surgical site infections (SSI). Infants born to women with BV have higher incidence of neonatal sepsis, respiratory distress, Neonatal Intensive Care Unit (NICU) admissions and low birth weight, as well as long-term adverse outcomes, irrespective of maternal peripartum infection. Prior studies have demonstrated that treating pregnant women with BV potentially reduces the risk of preterm labor. However, no studies have evaluated the impact of treating BV on the incidence of maternal peripartum infections, including chorioamnionitis, endometritis, and surgical site infection. The current standard of care is not to treat women with asymptomatic BV in pregnancy.

Our objective is to conduct a double-blinded placebo controlled, pragmatic randomized controlled trial of metronidazole (500 mg twice daily for 1 week) versus standard of care (i.e., no antibiotics, receipt of placebo) to prevent peripartum infection (primary composite inclusive of chorioamnionitis, endometritis, and surgical site infection, SSI) among pregnant non-laboring women enrolled after 34 weeks of gestation.

1.2 specific aims:

Primary aim 1: To determine if administration of a 7 days course of metronidazole 500 twice daily versus placebo to women with BV, regardless of symptoms, diagnosed clinically after 34 weeks reduces the incidence of peripartum infection inclusive of chorioamnionitis, endometritis, and SSI.

Secondary aims:

Secondary aim 1: To evaluate whether BV treatment affects the frequency of peripartum infection based on BV gram stain results at the time of randomization and labor admission.

Secondary aim 2: To evaluate whether BV treatment affects the frequency of intrapartum and postpartum fever, and individual infectious morbidities, as well as neonatal complications, including neonatal sepsis and NICU admission.

Secondary aim 3: To evaluate whether BV treatment affects the frequency of utilization of postpartum health care services, including maternal ER visits, postpartum clinic visits, OB triage visits, and postpartum hospital readmissions.

[figure not shown]

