2.3 Diagnosis of BV

The complex etiology of BV can contribute to an inaccurate diagnosis, especially in asymptomatic individuals in late pregnancy.(20) Microscopy of vaginal fluid has been a mainstay of office-based testing for vaginitis. A clinical diagnosis using Amsel criteria allows for a diagnosis at the bedside with prompt treatment. In addition, microscopic testing with Gram stain using Nugent score is considered the gold standard.(21) However, both methods require skilled staff and time and suffer from reduced sensitivity and specificity. Inaccurate BV results may lead to misdiagnosis and delays in treatment. NAATs can identify and differentiate between organisms associated with vaginitis and be a convenient point of care test, but remains to be validated in pregnancy.

Nucleic acid amplification tests (NAATs) to diagnose BV have been developed and its performance in comparison to gram stain and microscopy has been assessed outside of pregnancy among symptomatic and asymptomatic women. The Labcorp NAATs test includes Atrobium vaginae, BVAV-2, and Megasphaera-1, and in recent study of 100 non-pregnant individuals with and without vulvovaginal symptoms in gynecologic care, this test had a lower sensitivity but similar specificity (80 and 98%) compared to Amsel (99 and 99%) and gram stain (83 and 96%).(22) These studies have generally been conducted among samples of women seeking gynecologic care, family planning services, or testing for sexually transmitted diseases.

Because the performance of a diagnostic test varies according to the characteristics of the study population, studying the performance of a NAAT test in pregnancy is warranted. The prevalence of BV is known to decrease in late pregnancy in the setting of a changing hormonal milieu. The ideal test for women presenting with symptoms of vaginitis would have high sensitivity and specificity and would be available at the point of care.

2.4 Treatment of BV and obstetrical and surgical outcomes. The benefits of treating BV in pregnancy have been evaluated, but have been done in the setting of preterm birth prevention, and not to prevent peripartum infection. Hauth et al reported 18% decrease in the rate of preterm labor following treatment of BV in the 2nd and early 3rd trimesters in women with previous

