3.2 Secondary Research Questions

3.2.1: Does treatment of BV with 7-day course of metronidazole >34 weeks decrease the incidence of Gram stain +ve for BV at time of admission for labor?

[figure not shown]
Hypothesis : Treatment of BV will reduce the incidence of +ve Gram stain for BV at time of admission for labor.

3.2.2: Does treatment of BV with 7-day course of metronidazole >34 weeks decrease the incidence of neonatal complications including neonatal sepsis and NICU admission?

Hypothesis : Treatment of BV will reduce the incidence of neonatal complications.

3.2.3: Hypothesis : Does treatment of BV decrease utilization of health care services including maternal ER visits, postpartum clinic visits, OB triage visits, and postpartum hospital readmissions?

Hypothesis: Treatment of BV will reduce health care services utilization

4. STUDY DESIGN:

4.1 Study enrollment: We propose a double-blinded, placebo controlled, multi-center randomized trial of 482 pregnant women who are diagnosed with BV in late 3rd trimester (>34 weeks). During routine clinic visit after 34 weeks, prospective patients will be counseled about the study. Patients who agree to be enrolled, will sign informed consent.

Following enrollment, patients will be screened for BV. Those patients who are BV positive, will be randomized to receive either metronidazole 500 mg BID orally for 7 days or identically appearing placebo. The PI, Co-Investigators or study coordinators will be responsible for the informed consent.

1500 participants will be enrolled for screening to randomize 482 participants.

4.2 Study sites: This will be a multi-center, double-blinded randomized clinical trial. The primary site will be OSUWMC. The secondary center will be University of Texas Medical Branch, Galveston, Texas, and may include additional medical centers over time. The study period will be between November 2020 to September 2022. The number of subjects studied will be 482 patients. If a patient wishes to withdraw from study after randomization and receipt of study medications, no additional interventions will be performed, but we will collect study outcomes with patient consent as this is intent to treat study and patients' outcomes will be analyzed in the group they were assigned to.

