- Positive whiff-amine test, presence of fishy odor on adding a drop of 10% KOH
- Clue cells on wet mount

Patients who have at least 3 out of 4 of Amsel criteria will be considered positive for BV and will be randomized into either a control group or study group. Patient will be asked to characterize their vaginal discharge. Nitrazine paper will be used to assess PH. Saline will be added and light microscopy will be used to assess for clue cells and 10 % KOH will be added for whiff test.

Gram stain for BV: A gram stain will be collected from participants in clinic at time of screening and will be sent to the lab.

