7.3 Confirmation of therapy success

Following completion of therapy, patients admitted to labor and delivery will have 1 additional swab. The swabs can be collected by the provider during performing normal labor exam or it can be self-collected by the patient. This swab will be sent to the lab for another gram stain. However, results will not be used for clinical decision guidance. It will be used for analysis later.

7.4 Clinical care: The care of patients in the remaining antepartum period, intrapartum period, including the method of induction or augmentation of labor will be according to standard of care at the participating site, and per the managing clinical team. After a subject who meets inclusion criteria agrees to participation in our study, the obstetric team will contact one of the investigators. Signed informed consent will be obtained by the PI, Co-Investigators or study coordinators. The total participation time in the study will be considered terminated at 6 weeks postpartum. No additional antepartum or postpartum will be required for the study, only routine visits will be recommended.

7.5 Data collection: The data collected will be kept on a password-secured Ohio State Wexner Medical Center (OSUWMC) computer. An encrypted USB flash drive will be used to transfer data. The data will be linked to the patient by patient's MRN number. This identifier is needed to access and analyze demographic data. During analysis of the data, all identifiers will be deleted.

7.6 Informed consent. Under the direction of the PI, trained research staff will be available 24/7 to screen and consent patients according to study protocol. Patients will be enrolled in clinic at or after 34 weeks gestation.

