Analysis will be performed by intent to treat. Univariable and multivariable analysis will be used to describe the population in the study and to identify potential confounding variable. For this analysis normality will be tested using Shapiro-Wilk method. Demographics and descriptive statistics such as t test, Pearson's chi-square, and Mann-Whitney tests will be used as indicated. Incidence rates between the study groups will be compared using Chi-square or Fisher Exact tests as appropriate. Data will be either shown as median [IQR], mean \pm SD, or n (%). Given this is a RCT, multivariate logistic regression may be used to adjust for confounding variables, should there be evidence of unbalanced distribution of these variables despite randomization

Sample size was calculated using a superiority trial design. The primary outcome will be the proportion of subjects having the composite infectious outcome. Clark et al evaluated 390 laboring patients and reported the incidence of chorioamnionitis and postpartum endometritis in patients with BV to be 16.4 % in contrast to 8.1 % among those without BV. This is an underestimate since it did not include the surgical site infections and other infectious morbidity in the composite primary outcome. Assuming the rate of composite infectious morbidities in women with BV to be at least 17% and estimating treatment effect to be 50%, we estimate that a sample size of 482 patients will need to be enrolled to have sufficient power of 80%, at an alpha 0.05. Given estimated incidence of BV, enrolling 1500 patients will be needed, given that only 30% will be randomized.

Rate in Placebo	Effect size	Number per group for power		
		80%	85%	90%
17%	50%	241	275	321

Secondary analysis: Given our estimated baseline composite primary outcome is about 10% regardless of BV, assuming that in patients with BV, the outcome might be higher up to 20%. Analysis will be performed to assess if a sample size of 398 patients (199 per group) will be sufficient to demonstrate a similar difference in primary outcome.

Sample size calculation using baselines primary outcome in our institution.

Rate in Placebo	Effect size	Number per group for power		
		80%	85%	90%
20%	50%	199	227	266

STATA 14 (College Station, TX) will be used for statistical analysis. This trial will be registered with Clinical Trials Register (Clinicaltrials.gov), before recruitment is initiated and after IRB approval.

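### Secondary aim 1 judges the treatment effect on infection by a Gram stain taken after treatment, so that contrast is not randomized and hides any benefit achieved through BV clearance

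*Combined protocol and SAP*

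**What the plan says.** Section 1.2, Secondary aim 1, sets out to evaluate "whether BV treatment affects the frequency of peripartum infection based on BV gram stain results at the time of randomization and labor admission". Infection is the outcome, treatment is the contrast, and two Gram stains classify the women.

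The first stain is collected in clinic at screening, before study drug is given (7.1, 7.2). The second comes later: "Following completion of therapy, patients admitted to labor and delivery will have 1 additional swab" (7.3). Beyond excluding it from clinical decisions, 7.3 says of its use only "It will be used for analysis later".

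Research question 3.2.1 treats the same labor stain as an outcome, with the hypothesis "Treatment of BV will reduce the incidence of +ve Gram stain for BV at time of admission for labor".

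The secondary outcomes in 7.14 do not list the labor stain. Section 13 provides for intent-to-treat analysis, chi-square or Fisher tests, and optional logistic regression for imbalanced confounders. It gives no method for Secondary aim 1 and no caution about classifying women by a result obtained after randomization.

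**The concern.** The natural reading of the aim is a comparison of metronidazole with placebo within strata of each stain. For the screening stain this is an ordinary baseline subgroup analysis. For the labor stain it is not, because the trial expects treatment to decide who falls in which stratum. Two things follow.

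- **Attenuation.** If treatment prevents infection by clearing BV, the labor stain lies on the causal path. Holding it fixed removes that part of the effect.
- **Selection.** Women still Gram-positive after metronidazole need not resemble women Gram-positive after placebo. Any shared cause of a positive labor stain and of infection then confounds the contrast.

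The report could show little or no effect in either stratum for a treatment that works, or a difference produced by selection alone. A reader could take the first as evidence against the treatment.

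**Working it through.** **1. The plan's own figure.** With 17% v 8.5%, two-sided alpha 0.05, 80% power and no continuity correction:

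n = [1.96·√(2·0.1275·0.8725) + 0.8416·√(0.17·0.83 + 0.085·0.915)]² / 0.085² = 240.5, so 241 per group and 482 in total. This matches section 13, and nothing below alters it.

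**2. Attenuation, effect wholly through the stain.** Section 13 cites infection "in patients with BV to be 16.4 % in contrast to 8.1 % among those without BV". Let g be the share Gram-positive at labor; infection in an arm is g·16.4 + (1 − g)·8.1. The documents give no values of g, so these are assumed.

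- Positivity 70% on placebo, 30% on metronidazole: 0.7·16.4 + 0.3·8.1 = 13.91% v 0.3·16.4 + 0.7·8.1 = 10.59%; overall RR 0.761.
- Positivity 90% v 20%: 0.9·16.4 + 0.1·8.1 = 15.57% v 0.2·16.4 + 0.8·8.1 = 9.76%; overall RR 0.627.

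In both cases women with the same labor stain have the same risk in either arm, so each within-stratum RR is 1.00.

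**3. Attenuation, effect partly through the stain.** Suppose the overall RR is the planned 0.50 and treatment also has a constant direct RR d in both strata. Then overall RR = d × mediated RR.

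- d = 0.50/0.761 = 0.66, with ln 0.761/ln 0.50 = 39% of the log effect through the stain.
- d = 0.50/0.627 = 0.80, with 67% through the stain.

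The strata would show 0.66 or 0.80, not 0.50. The ratio 8.1/16.4 = 0.49 is close to the planned 50% effect, but the plan does not say where the 50% comes from; any link is inference.

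**4. Selection, no drug effect on infection.** All inputs are assumed. Half the women have 24% risk and half 10% (17% overall in both arms). On placebo the stain is positive in 80% of the higher-risk and 60% of the lower-risk women.

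*Metronidazole positivity 50%/10%:*
- Gram-positive: (0.5·0.5·0.24 + 0.5·0.1·0.10)/0.30 = 21.67% v (0.5·0.8·0.24 + 0.5·0.6·0.10)/0.70 = 18.00%; RR 1.20.
- Gram-negative: 15.00% v 14.67%; RR 1.02.

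*Metronidazole positivity 40%/15%:*
- Gram-positive: 20.18% v 18.00%; RR 1.12.
- Gram-negative: 15.79% v 14.67%; RR 1.08.

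**5. Both together.** Take labor positivity of 20% v 80% and an assumed unmeasured factor, present in half the women, that doubles infection risk.

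- If the factor raises labor positivity, an overall RR of 0.67 becomes 1.12 to 1.18 in Gram-positive and 1.15 to 1.25 in Gram-negative women.
- If it lowers positivity, an overall RR of 0.65 becomes 0.80 and 0.85.

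The net direction of bias is therefore not fixed.

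**6. What the screening stain can support.** Under 7.2, "Patients who have at least 3 out of 4 of Amsel criteria will be considered positive for BV and will be randomized", so every randomized woman is Amsel-positive and few may be Gram-negative. Section 2.3 gives sensitivity and specificity of 99%/99% for Amsel and 83%/96% for Gram stain, in non-pregnant women. Assume 30% prevalence and independent errors:

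Gram-negative share = (0.297·0.17 + 0.007·0.96)/(0.297 + 0.007) = 0.188; × 241 = 45 per arm, leaving 196 Gram-positive.

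Interaction test on log RR (Wald, two-sided 0.05), with 17% v 8.5% in Gram-positive women and RR 1 in Gram-negative women:

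- Variance, Gram-positive: 0.83/(196·0.17) + 0.915/(196·0.085) = 0.0798.
- Variance, Gram-negative: 2·0.83/(45·0.17) = 0.2170 at 17% risk, or 2·0.919/(45·0.081) = 0.5043 at 8.1% risk.
- z = 0.693/√0.2968 = 1.27, power 25%; or z = 0.693/√0.5841 = 0.91, power 15%.

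Simulation on the log-odds scale gives 22% and 13%. With a Gram-negative share of 10% to 30%, power is 11% to 31% (Wald) or 6% to 28% (simulation).

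**The case against.** The strongest reply is that the plan never specifies the analysis criticized here. The aim's wording is loose, and neither section 13 nor 7.14 describes arm contrasts within labor-stain strata. Question 3.2.1 uses the labor stain validly, as an outcome; 7.3 is headed as confirming therapy success; and 3.2.2 and 3.2.3 match Secondary aims 2 and 3 in order, so 3.2.1 may be the working form of aim 1. That may well be the intent. It does not settle the matter, because 3.2.1 has a different outcome and omits the randomization stain. If 3.2.1 is meant, the aim is misworded; if it is not, the contrast is invalid as a treatment effect. The sentence needs changing either way.

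Other points stand as limits on size:

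- Clearance rates, risk split and stain shares are assumed. The full-mediation examples give placebo infection of 13.9% and 15.6%, below the planned 17%, and give cleared women the risk of women who never had BV.
- The spurious ratios are modest against precision. In the first selection case, about 72 v 169 Gram-positive women, the 95% confidence interval spans a factor of about 1.7 either way.
- The 19% Gram-negative share ignores intermediate stains and the use of self-collected swabs and self-described discharge (7.1, 7.2). The wider power range is the safer guide.
- The aim is secondary.

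It can also be said that the low-powered interaction is not needed to repair the defect. That is fair; it is simply the only randomized form of the infection question that the aim asks.

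**Conclusion.** The concern holds. By the plan's own account the labor-admission stain follows treatment and is expected to respond to it, so arm contrasts within its strata are not protected by randomization. They remove the part of the effect that acts through clearance: all of it only if the labor stain wholly mediates the effect, part of it otherwise. Selection can add to, offset or reverse the remainder. This rests on timing and on the plan's hypothesis, not on the illustrative numbers, and the documents do not allow the size to be fixed.

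The consequence is confined to a secondary aim. The change should be made, with medium confidence about its practical weight because the intended analysis is not spelled out.

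**What to change.** - Reword Secondary aim 1 so that the treatment effect on infection is examined by screening Gram stain only. Use an arm-by-screening-stain interaction, stated in advance to be low-powered.
- In section 13, say that the labor-admission stain is compared between randomized arms as an outcome, in line with 3.2.1.
- Label any table of infection by labor stain as descriptive, not as a treatment effect. A mediation or principal-stratum analysis is optional and would need its assumptions stated.

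This takes one sentence in the aims and one in section 13, with no new data and no change in sample size. The price is that infection by clearance status is no longer reported as a simple treatment contrast. Making the change before unblinding also avoids a data-dependent choice between the two readings.

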2. BACKGROUND

2.1 Bacterial vaginosis is a frequent condition in pregnancy. Bacterial vaginosis (BV) is the most common cause of vaginal discharge among reproductive aged women (1). In the United States, the prevalence of BV is estimated to be 30 %. Prevalence varies with ethnicity, including 50% in African Americans, 30% in Mexican Americans, and 24% in non-Hispanic whites. In obese women (BMI>30), its prevalence exceeds 35% (2). Even in women with an intermediate gram stain, the rate of BV is estimated to be 18% (4). Despite its high frequency in pregnancy and its known impact on adverse pregnant outcomes, it remains a complex, poorly understood clinical syndrome. BV is considered to result in an imbalance between naturally existing vaginal flora. There is a decrease in hydrogen peroxide secreting lactobacilli and an increase in pathogenic anaerobic bacteria including *Gardnerella vaginalis*, *Ureaplasma urealyticum*, and *Mycoplasma hominis*.

Several studies have evaluated the adverse effects of BV on maternal and infant outcomes. Gravett et al. reported that pregnant women with BV are at an increased risk of chorioamnionitis (OR 2.1), preterm labor (OR 2.2), premature rupture of membranes (PROM) (OR 2.4), and low birth weight (OR 1.7) (3). Similarly, Clark et al. evaluated 390 laboring women and found that pregnant with BV had a 2-fold frequency of chorioamnionitis and postpartum endometritis (16%) compared to women with a negative gram stain (8%). BV is also associated with adverse infant outcomes. Dingens et al. found that term infants born to women with BV were more likely to have respiratory distress (OR 1.28), suspected neonatal sepsis (OR 1.6) and NICU admission (OR 1.4), independent of maternal chorioamnionitis (5).

2.2 Peripartum infection increases the risk of adverse pregnancy outcomes. Peripartum infection is the 2nd leading cause of maternal mortality. Having a peripartum infection increases the risk for developing another peripartum infection, and ultimately, maternal sepsis and death (Figure 1).

Chorioamnionitis is an infectious and/or inflammatory disorder of chorion, amnion or both (6). Overall incidence in term pregnancies in an era of GBS prophylaxis is <5%, though the incidence increases up to 12% in laboring women who have a primary cesarean delivery. Multiple organisms have been isolated from chorioamnionitis patients. Notably, the most common organism found on PCR among women with chorioamnionitis is *Gardnerella vaginalis* followed by *Ureaplasma urealyticum* (10), the organisms that contribute to BV. Chorioamnionitis itself increases the risk of adverse maternal and fetal outcomes. Maternal complications of chorioamnionitis include: uterine atony (RR 2.5), pelvic abscess (RR 3.7), septic thrombophlebitis (RR 2.7), thromboembolism (RR 1.49), hysterectomy (RR 1.57) and need for blood transfusion (RR 2.25). Neonatal complications include: confirmed neonatal sepsis (RR 2.9), low Apgar score at 1 minute < 3 (RR 2.09) and neonatal seizures (2.7). (7, 8) Additionally, longer term infant outcomes, including cerebral palsy, are higher with chorioamnionitis (OR 2.4). (9)

Endometritis is defined as postpartum infection of the endometrial lining that can extend to the myometrium and parametrium. It remains one of the most common infectious complication in the peripartum period estimated to affect nearly a tenth of all pregnancies (11). Notably, endometrial cultures on patients diagnosed with postpartum endometritis have found that one of the most common organisms is *Gardnerella vaginalis* (12).

SSI is defined as infection occurring within 30 days of surgery occurring at the incision site site superficially or deep or affecting an organ that was manipulated during surgery. BV micro-organisms are commonly isolated from surgical sites in women undergoing gynecologic procedures. Addition of metronidazole to preoperative antibiotic regimen in patients with BV has shown in many studies to reduce SSI, with a significant reduction ranging from 2 to 3 fold (18).

